4. STUDY DESIGN

4.1. General Design

The study is a Phase 2/3, 2-part, randomized, observer-blind, active-controlled, multicenter study to evaluate the immunogenicity and safety of mRNA-1273.529 and mRNA-1273.214 booster vaccine in medically stable individuals 16 years and older. The mRNA-1273.529 vaccine to be tested in this study contain mRNAs encoding for the S-2P of the SARS-CoV-2 Omicron variant (B.1.1.529). The mRNA-1273.214 vaccine contains the Wuhan Hu-1 and B.1.1.529 mRNAs (2 mRNAs: CX024414 encoding for the S-2P of Wuhan Hu-1 and CX-031302 encoding for the S-2P of B.1.1.529) and formulated in the same LNP.

The study consists of 2 parts with 2 phases each:

In **Part 1**, approximately 600-1000 participants will be randomized in a 1:1 ratio to 1 of 2 study arms to receive a single dose of either 50 μ g of mRNA-1273.529 or 50 μ g of mRNA-1273 (active control). Randomization will be stratified by age groups (16 to < 65 years or \geq 65 years) and number of booster doses received (to receive study vaccine as the 4th dose or to receive study vaccine as the 3rd dose). At least \geq 90% of participants will receive study vaccine as the 4th dose. The potential number of participants in each arm and the randomization ratio can be found in [Table 5](#).

In **Part 2**, approximately 2,924 participants will be randomized in a 1:1 ratio to 1 of 2 study arms to receive a single dose of either 50 μ g of mRNA-1273.214 or 50 μ g of mRNA-1273 (active control). Randomization will be stratified by age groups (16 to < 65 years or \geq 65 years) and number of booster doses received (to receive study vaccine as the 4th dose or to receive study vaccine as the 3rd dose). At least \geq 90% of participants will receive study vaccine as the 4th dose. The potential number of participants in each arm and the randomization ratio can be found in [Table 6](#).

Each part has a Phase A (randomized, blinded) and Phase B (open-label, observational). Phase B was designed to offer eligible participants in either treatment arms in Part 1 to obtain an additional booster after their Month 6 assessment and eligible participants in either treatment arms in Part 2 the option to obtain an additional booster after their Month 3 assessment. The additional booster may be obtained outside the study.

Table 5: Part 1 Study Arm and Dose Levels

Vaccination Group	Vaccination Received	Total Dose	N (total)	Study vaccine as the 3 rd dose	Study vaccine as the 4 th dose
1	mRNA-1273.529	50 µg	300-500 ^a	30-50	270-450
2	mRNA-1273 (Active Control)	50 µg	300-500 ^a	30-50	270-450

Abbreviations: mRNA = messenger ribonucleic acid; N = number.

^a Part 1 will end enrollment when Part 2 starts enrollment. The number of participants in Part 1 will be determined by the start date of Part 2.

Table 6: Part 2 Study Arm and Dose Levels

Vaccination Group	Vaccination Received	Total Dose	N (total)	Study Vaccine as the 3 rd Dose	Study Vaccine as the 4 th Dose
1	mRNA-1273.214	50 µg	1462	134	1328
2	mRNA-1273 (Active control)	50 µg	1462	134	1328

Abbreviations: mRNA = messenger ribonucleic acid; N = number.

All participants will have previously received 2 or 3 doses of an authorized/approved COVID-19 vaccine. Participants who had previously received 2 doses of a COVID-19 vaccine as a primary series will receive mRNA-1273.529, mRNA-1273.214, or mRNA-1273 as the third dose, and participants who have previously received a primary series and 1 booster dose will receive mRNA-1273.529, mRNA-1273.214, or mRNA-1273 as the 4th dose. Participants who will receive the 4th dose as part of the study must have previously received a mRNA vaccine as the 3rd dose of a COVID-19 vaccine. Participants who will receive the 3rd dose as part of the study may have previously received 2 doses of a mRNA or a non-mRNA COVID-19 vaccine (a mixed approach is acceptable).

Medically stable individuals, ages 16 and above (to include 2 age groups: 16 to < 65 and ≥ 65 years) will be screened and enrolled. Participants with chronic diseases requiring ongoing medical intervention or within the last 2 months prior to enrollment will be excluded.

Participants with immunocompromising conditions or medications, or malignancy within 10 years (excluding nonmelanoma skin cancer) will also be excluded. Participants who received a COVID-19 vaccine within 90 days prior to enrollment or had positive SARS-CoV-2 testing by an authorized/approved lateral flow/rapid antigen or polymerase chain reaction (PCR) within 90 days prior to enrollment will be excluded as well.

Except for appropriately delegated unblinded pharmacists, vaccine administrators and monitors, all personnel involved in the conduct of the trial will remain blinded to individual treatment assignment until study unblinding. Study visits will consist of a Screening Visit (up to 28 days before the Day 1 visit), Vaccination Visit at Day 1 and subsequent study visits on Day 8 (for a subset of participants in Part 2), Day 29 (Month 1), Day 85 (Month 3), Day 179 (Month 6), and

Day 359 (Month 12), with up to 13 months of study participation. Unscheduled visits for potential symptoms of COVID-19 will include PCR testing.

4.2. Scientific Rationale for Study Design

This 2-phase study includes a randomized, blinded phase (Phase A) and an open-label, observational phase (Phase B). Phase A is designed as a 2-part, randomized, stratified, observer-blind, active-controlled study to demonstrate the immunogenicity and safety of the mRNA-1273.529 and mRNA-1273.214 vaccine in medically stable individuals 16 years and older. Participants will receive a single dose of either mRNA-1273.529/mRNA-1273.214 or mRNA-1273 (active comparator) booster vaccine as the 3rd or 4th dose of a COVID-19 vaccine.

Because it is possible that participants are exposed to SARS-CoV-2 through community exposure, NP swab samples and the serologic assays will be collected before vaccination on Day 1 to help discriminate between natural infection and vaccine-induced antibody responses, should such discrimination be needed. Furthermore, NP swab specimen(s) for assessment of pathogens including SARS-CoV-2, will also be collected at any time during the study period if participants have symptoms suggestive of COVID-19 or other upper or lower respiratory infection at the investigator's discretion. Additionally, clinical information will be collected to evaluate the severity of the clinical case.

Following authorization of the mRNA-1273.214 booster, the study was amended to allow a transition to Phase B, the open-label, observational phase. Transitioning the study to the open-label, observational phase allows eligible participants in either treatment arm in Part 1 and Part 2 to receive an additional booster outside of the study after completing the Month 6 and Month 3 study visit, respectively.

4.3. Justification for Dose and Control Product

The Sponsor developed mRNA-1273, an mRNA-based vaccine against SARS-CoV-2. Having achieved the primary endpoint in a pivotal Phase 3 study conducted in persons at high risk for SARS-CoV-2 infection in December 2020, mRNA-1273 was granted EUA for the prevention of COVID-19 for individuals 18 years of age and older based on the demonstration of efficacy and safety in a pivotal Phase 3 study ([Baden et al 2021](#)). Given the potential for waning immunity, the emergence of highly transmissible SARS-CoV-2 variants, and the ability of some variants to partially escape immunity, the Sponsor assessed the immunogenicity and safety of a 50 µg booster immunization. Administration of a booster dose of 50 µg at least 6 months after administration of the second of 2 doses of the mRNA-1273 primary series greatly enhanced immune responses compared to pre-boost levels. Additionally, no new safety signals emerged upon administration of the 50 µg booster dose (Phase 2 mRNA-1273-P201; NCT04405076). Based on cumulative evidence, the benefit-risk profile of a 50 µg booster dose of mRNA-1273 is

favorable, particularly in light of increasing breakthrough disease with the emergence of the Delta/Omicron variants. The FDA has authorized the emergency use administration of a single booster dose (50 μ g) of mRNA-1273 vaccine at least 5 months after completing the primary series of this vaccine in individuals 18 years of age and older.

Based on the Sponsor's prior studies as described above with mRNA-1273, a dose level of 50 μ g for mRNA-1273.529 and mRNA-1273.214 was selected and is anticipated to be immunogenic and well tolerated.

4.4. End of Study Definition

The end of study (EoS) is defined as completion of the last visit of the last participant in each part of the study or last scheduled procedure as shown in the schedule of events (SoE) [Table 1](#) for Part 1 and [Table 2](#) for Part 2) for the last participant in the study.

A participant is considered to have completed the study only if they complete the final visit on Day 359 (Month 12) as shown in the SoE ([Table 1](#) and [Table 2](#)).

5. STUDY POPULATION

Prospective approval of protocol deviations to recruitment and enrollment criteria, also known as protocol waivers or exemptions, is not permitted.

5.1. Inclusion Criteria

Each participant must meet all of the following criteria during the screening period and at Day 1, unless noted otherwise, to be enrolled in this study:

1. Is male or female, at least 16 years of age at the time of consent (Screening Visit).
2. Investigator's assessment that the participant understands and is willing and physically able to comply with protocol-mandated follow-up, including all procedures.
3. Participant has provided written informed consent for participation in this study, including all evaluations and procedures as specified in this protocol.
4. Female participants of nonchildbearing potential may be enrolled in the study. Nonchildbearing potential is defined as postmenopausal or permanently sterilized ([Section 11.2](#)). A Follicle stimulating hormone (FSH) level should be measured at the discretion of the investigator to confirm postmenopausal status, if necessary.
5. Female participants of childbearing potential may be enrolled in the study if the participant fulfills all the following criteria:
 - Has a negative pregnancy test at the Screening Visit and on the day of vaccination prior to vaccine dose being administered on Day 1.
 - Has practiced adequate contraception or has abstained from all activities that could result in pregnancy for at least 28 days prior to the first dose (Day 1). Adequate female contraception is defined as consistent and correct use of a local health authority approved contraceptive method in accordance with the product label.
 - Has agreed to continue adequate contraception through 90 days following vaccine administration.
6. Has received 2 prior doses of one of the following approved/authorized COVID-19 vaccines: Moderna, Pfizer/BioNTech, Oxford/AstraZeneca, Janssen. A heterologous vaccine regimen is acceptable.
7. Participants who will receive the 4th dose as part of the study must have previously received a mRNA vaccine (Moderna or Pfizer/BioNTech) as the 3rd dose of a COVID-19 vaccine. Participants who will receive the 3rd dose as part of the study may have previously received 2 doses of an approved/authorized mRNA or a non-mRNA COVID-19 vaccine (a heterologous vaccine regimen is acceptable).

5.2. Exclusion Criteria

Participants meeting any of the following criteria, unless noted otherwise, will be excluded from the study:

1. Had close contact (without personal protective equipment [PPE]) as defined by the CDC in the past 14 days to someone diagnosed with SARS-CoV-2 infection or COVID-19 within 10 days of the close contact. Participants may be rescreened after 14 days provided that they remain asymptomatic.
2. Participant is acutely ill or febrile (temperature $\geq 38.0^{\circ}\text{C}/100.4^{\circ}\text{F}$) 72 hours prior to or at the Screening Visit or Day 1. Participants meeting this criterion may be rescheduled within the 28-day screening window and will retain their initially assigned participant number.
3. Has tested positive for SARS-CoV-2 by an authorized/approved lateral flow/rapid antigen or PCR test within 90 days of Screening.
4. Has received a COVID-19 vaccine within 90 days of the Screening Visit.
5. Has received a total of 4 doses or more of COVID-19 vaccine.
6. Has received a COVID-19 vaccine at a dose different from the authorized/approved dose.
7. History of a diagnosis or condition that, in the judgment of the Investigator, is clinically unstable or may affect participant safety, assessment of safety endpoints, assessment of immune response, or adherence to study procedures. Clinically unstable is defined as a diagnosis or condition requiring significant changes in management or medication within the 2 months prior to screening and includes ongoing workup of an undiagnosed illness that could lead to a new diagnosis or condition.
8. Reported history of congenital or acquired immunodeficiency, immunosuppressive condition, or immune-mediated disease requiring immunosuppressive treatment or other immunosuppressive condition.
9. Dermatologic conditions that could affect local solicited AR assessments (eg, tattoos, psoriasis patches affecting skin over the deltoid areas).
10. Reported history of anaphylaxis or severe hypersensitivity reaction after receipt of any components of mRNA vaccine.
11. Reported history of bleeding disorder that is considered a contraindication to intramuscular (IM) injection or phlebotomy.
12. Any medical, psychiatric, or occupational condition, including reported history of substance abuse, that, in the opinion of the Investigator, might pose additional risk due to participation in the study or could interfere with the interpretation of study results.

13. Has received systemic immunosuppressants or immune-modifying drugs for > 14 days in total within 181 days prior to screening (for corticosteroids \geq 10 mg/day of prednisone or equivalent) or is anticipating the need for immunosuppressive treatment at any time during participation in the study.
14. Has received or plans to receive any licensed vaccine \leq 28 days prior to the study injection (Day 1) or plans to receive a licensed vaccine within 28 days after the study injection (with the exception that approved seasonal influenza vaccine may be received by at least 7 days and preferably 14 days apart from the study injection).
15. Has received systemic immunoglobulins or blood products within 90 days prior to the Screening Visit or plans to receive during the study.
16. Diagnosis of malignancy within the previous 10 years (excluding nonmelanoma skin cancer).
17. Has donated \geq 450 mL of blood products within 28 days prior to the Screening Visit or plans to donate blood products during the study.
18. Has participated in an interventional clinical study within 28 days prior to the Screening Visit based on the medical history interview or plans to do so while participating in this study.
19. Is an immediate family member or household member of study personnel, study site staff, or Sponsor personnel.

5.3. Lifestyle Restrictions

Participants must not eat or drink anything hot or cold within 10 minutes before oral temperature is taken.

5.4. Screen Failures

Screen failures are defined as participants who consent to participate in the clinical study but are not subsequently randomly assigned to treatment. A minimal set of screen failure information is required to ensure transparent reporting of screen failure participants to meet the Consolidated Standards of Reporting Trials publishing requirements and to respond to queries from regulatory authorities. Minimal information includes date of informed consent, demography, screen failure details, eligibility criteria, and information on any SAE which may have occurred from the time informed consent was obtained to the time of withdrawal.

Individuals who do not meet the criteria for participation in this study (screen failure) may be rescreened one time if they will be eligible upon rescreening.

6. STUDY TREATMENT

6.1. Investigational Product and Active Comparator Administered

The vaccines to be administered in this study are described in [Table 7](#).

Table 7: Investigational Product and Active Comparator Administered

Study Arm:	mRNA-1273	mRNA-1273.529	mRNA-1273.214
Intervention Name:	mRNA-1273 (aka, Moderna COVID-19 Vaccine)	mRNA-1273.529	mRNA-1273.214
Type:	Vaccine	Vaccine	Vaccine
Dosage Level(s):	50 µg (mRNA)	50 µg (mRNA)	50 µg (mRNA)
Route of Administration:	IM injection	IM injection	IM injection
Physical Description:	Sterile liquid for injection, white-to-off-white dispersion	Sterile liquid for injection, white-to-off-white dispersion	Sterile liquid for injection, white-to-off-white dispersion
Source:	Sourced locally by the sites	Provided centrally by the Sponsor	Provided centrally by the Sponsor
Packaging and Labeling:	mRNA-1273 will be provided in its commercial presentation	mRNA-1273.529 will be provided in 2R borosilicate glass vials. Vials will be labeled as required per local requirement.	mRNA-1273.214 will be provided in 2R borosilicate glass vials. Vials will be labeled as required per local requirement.

Abbreviations: IM = intramuscular; mRNA = messenger ribonucleic acid.

mRNA-1273 is a LNP dispersion of an mRNA encoding the prefusion stabilized S protein of SARS-CoV-2.

mRNA 1273.529 contains mRNA CX-031302 encoding for the S-2P of the SARS-CoV-2 Omicron variant (B.1.1.529). mRNA 1273 contains mRNA CX-024414 encoding for the S-2P of Wuhan-Hu-1. mRNA-1273.214 is a bivalent vaccine containing mRNA-1273.529 and mRNA-1273 co-formulated at a 1:1 ratio. mRNA-1273.529, mRNA-1273, and mRNA-1273.214 each consists of mRNAs formulated in a mixture of 4 lipids common to the Sponsor's mRNA vaccine platform: SM-102, cholesterol, DSPC, and PEG 2000 DMG.

mRNA-1273.529, mRNA-1273, and mRNA-1273.214 will be administered at a 50 µg dose level as an IM injection into the deltoid muscle on Day 1.

6.2. Randomization and Blinding

Randomization during the blinded Phase (Phase A) will be performed using an interactive response technology (IRT). In Part 1, approximately 600-1000 participants will be randomized in a 1:1 ratio to receive a single dose of either 50 µg of mRNA-1273.529 or 50 µg of mRNA-1273 (active control). In Part 2, approximately 2,924 participants will be randomized in a 1:1 ratio to receive a single dose of either 50 µg of mRNA-1273.214 or 50 µg of mRNA-1273 (active control). In both parts, randomization will be stratified by age groups (16 to < 65 years or ≥ 65 years) and number of booster doses received (to receive study vaccine as the 4th dose or to receive study vaccine as the 3rd dose). At least ≥ 90% of participants will receive study vaccine as the 4th dose.

As the appearance of the study vaccines differ, enrollment will be observer-blinded as to treatment assignment.

Dose preparation, administration, and accountability will be performed by designated unblinded site personnel who will not participate in any of the clinical study evaluations. The unblinded site personnel will prepare the dose out of view of the participant and the blinded site personnel. These personnel will have no study functions other than investigational product (IP) management, documentation, accountability, preparation, and administration. They will not be involved in participant evaluations and will not reveal the identity of the IP to either the participant or the blinded clinic personnel involved in the conduct of the study unless this information is necessary in the case of an emergency. Once the injection is completed, only the blinded clinic staff will perform further assessments and interact with the participants. Access to the randomization code will be strictly controlled at the pharmacy.

Unblinded site monitors, not involved in other aspects of monitoring, will be assigned as the IP accountability monitors. They will have responsibilities to ensure that sites are following all proper IP accountability, preparation, and administration procedures.

The laboratory personnel in charge of immunogenicity testing will be blinded to the treatment assignment of the samples tested throughout the course of the study.

Except in the case of medical necessity and optional unblinding ([Section 6.3.7](#)), a participant's treatment should not be unblinded without the approval of the Sponsor. The treatment code should be broken only if the investigator in charge of the participant feels that the case cannot be treated without knowing the identity of the study vaccine. Instructions regarding emergency unblinding will be provided to the investigator and are discussed in [Section 6.3.7](#).

The investigator, clinic staff, study participants, site monitors, and Sponsor personnel (or its designees) will be blinded to the IP administered until the unblinding occurs ([Section 6.3.7](#)) or until study database is locked and unblinded for the final analysis. At the planned analyses (see [Section 9.7](#)), pre-identified Sponsor team members and selected contract research organization (CRO) team members will be unblinded to conduct the analyses.

6.3. Preparation/Handling/Storage/Accountability

6.3.1. Clinical Study Material Preparation

The IP will be prepared for each participant based on their vaccination group assignment. The mRNA-1273.529 vaccine injection will have a volume of 0.25 mL and will contain mRNA-1273.529 at a dose of 50 µg. The mRNA-1273.214 vaccine will have a volume of 0.25 mL and will contain mRNA-1273.214 at the dose of 50 µg. The active comparator (mRNA-1273) will be administered at a volume of 0.25 mL and will contain mRNA-1273 at a dose of 50 µg. The mRNA-1273.529, mRNA-1273.214, and mRNA-1273 preparation instructions are detailed in the Pharmacy Manual.

6.3.2. Clinical Study Material Administration

The study vaccine will be administered as a single IM injection into the deltoid muscle on Day 1. Preferably, the IP should be administered into the nondominant arm.

Participants will be monitored for a minimum of 15 minutes after administration of the study injection. Assessments will include vital sign measurements and monitoring for local or systemic reactions as shown in the SoE ([Table 1](#) and [Table 2](#)).

The clinic will be appropriately staffed with individuals with basic cardiopulmonary resuscitation training/certification. Either onsite resuscitation equipment and personnel or appropriate protocols for the rapid transport of a participant to a resuscitation area or facility are required.

Further instructions for the preparation and administration of mRNA-1273.529, mRNA-1273.214, and active comparator (mRNA-1273) are described in the Pharmacy Manual.

6.3.3. Clinical Study Material Packaging and Labeling

The Sponsor will provide the investigator (via the clinic pharmacy) with adequate quantities of the IP.

mRNA-1273.529 is provided as a sterile solution for injection at a concentration of 0.2 mg/mL in 20 mM Tris buffer with sucrose, at pH 7.5 and presented in 2R United States Pharmacopeia (USP) Type I borosilicate glass vials with PLASCAP vial seal containing a 13 mm FluroTec

coated plug stopper with a 0.8 mL nominal fill volume. mRNA-1273.529 will have all required labeling per regulations and will be supplied to the pharmacy in an unblinded manner.

mRNA-1273.214 is provided as a sterile solution for injection at a concentration of 0.1 mg/mL in 20 mM Tris buffer with sucrose, at pH 7.5 and presented in 2R United States Pharmacopeia (USP) Type I borosilicate glass vials with PLASCAP vial seal containing a 13 mm FluroTec coated plug stopper with a 0.8 mL nominal fill volume. mRNA-1273.214 will have all required labeling per regulations and will be supplied to the pharmacy in an unblinded manner.

mRNA-1273 injection will be sourced locally as commercial supply.

All IPs used in this study will be prepared, packaged, and labeled in accordance with the standard operating procedures of the Sponsor or those of its designee, Code of Federal Regulations Title 21, Good Manufacturing Practice guidelines, International Council for Harmonisation (ICH) Good Clinical Practice (GCP) guidelines, guidelines for Quality System Regulations, and applicable regulations.

Updates to this clinical study material packaging and labeling information may be provided in the Pharmacy Manual or associated Commercial Packaging and will supersede the information provided in the protocol.

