mRNA-1273.214 contains CX-024414, the mRNA that encodes for the prefusion stabilized spike glycoprotein (S-2P) of the Wuhan-Hu-1 isolate of SARS-CoV-2, and CX-031302, the mRNA that encodes for the S-2P of the SARS-CoV-2 B.1.1.529 variant. The formulated mRNAs are mixed in a 1:1 ratio. mRNA-1273.214 consists of each mRNA formulated in a mixture of four lipids common to the Sponsor's mRNA vaccine platform: SM-102, cholesterol, DSPC, and PEG 2000-DMG.				
mRNA-1273.529, mRNA-1273.214, and mRNA-1273 will be administered at a 50 µg dose level as an IM injection into the deltoid muscle on Day 1.				
Procedures and Assessments:				

Immunogenicity Assessments:

Blood samples will be collected for the following parameters:

- Serum binding antibody (bAb) level against SARS-CoV-2 as measured by ligand binding assay specific to the SARS-CoV-2 S protein and the S protein receptor-binding domain (RBD).
- Serum neutralizing antibody (nAb) level against SARS-CoV-2 as measured by pseudovirus neutralization assays.
- Testing for serologic markers for SARS-CoV-2 infection as measured by anti-nucleocapsid antibodies detected by immunoassay.

Safety Assessments:

Safety assessments will include monitoring and recording of the following for each participant:

- Solicited local and systemic adverse reactions (ARs) that occur during the 7 days following vaccination (ie, the day of injection and 6 subsequent days). Solicited ARs will be recorded daily using eDiaries.
- Unsolicited adverse events (AEs) observed or reported during the 28 days following vaccination. Unsolicited AEs are AEs that are not included in the protocol-defined solicited ARs.
- AEs leading to withdrawal from the study.
- Medically attended AEs (MAAEs) from vaccination on Day 1 through end of study (EoS) or withdrawal from the study.
- AEs of special interest (AESIs) from vaccination on Day 1 through EoS or withdrawal from the study.
- Serious AEs (SAEs) from vaccination on Day 1 through EoS or withdrawal from the study.
- Vital sign measurements before and after vaccination.
- Physical examination findings (if performed).
- Assessments for SARS-CoV-2 infection from Day 1 through study completion.
- Details of all pregnancies in female participants will be collected after the start of study vaccine and until the end of their participation in the study. All pregnancies must be

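### For mRNA-1273.214 the stated volume, dose and concentration differ by a factor of 2 unless 0.1 mg/mL means each mRNA separately, which the documents never say

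*Protocol*

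**What the plan says.** Protocol Section 6.3.1 (preparation) fixes volume and dose for the test product: "The mRNA-1273.214 vaccine will have a volume of 0.25 mL and will contain mRNA-1273.214 at the dose of 50" µg. It gives the same pair for the control: "The active comparator (mRNA-1273) will be administered at a volume of 0.25 mL and will contain mRNA-1273 at a dose of 50" µg. The monovalent product, mRNA-1273.529, also has 0.25 mL and 50 µg.

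Section 6.3.3 (packaging) gives concentrations for the two sponsor-supplied products. For the monovalent one, "mRNA-1273.529 is provided as a sterile solution for injection at a concentration of 0.2 mg/mL". For the bivalent one, "mRNA-1273.214 is provided as a sterile solution for injection at a concentration of 0.1 mg/mL". Both come in vials with a 0.8 mL nominal fill. No concentration is given for mRNA-1273, which is sourced locally.

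Composition is described in three places. The synopsis says "The formulated mRNAs are mixed in a 1:1 ratio". Section 4.1 says the two mRNAs share one lipid nanoparticle. Section 6.1 says "mRNA-1273.214 is a bivalent vaccine containing mRNA-1273.529 and mRNA-1273 co-formulated at a 1:1 ratio". Table 7 in Section 6.1 expresses the dosage level of all three vaccines as 50 µg of mRNA.

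Sections 6.3.1 and 6.3.2 refer to the Pharmacy Manual for preparation instructions, and Section 6.3.3 adds: "Updates to this clinical study material packaging and labeling information may be provided in the Pharmacy Manual or associated Commercial Packaging and will supersede" what the protocol gives. The SAP repeats the 50 µg dose but gives no volume or concentration.

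**The concern.** Volume, concentration and dose are tied by one multiplication. For mRNA-1273.214 the three printed figures satisfy it only if the concentration refers to each mRNA separately. Nothing in either document says so.

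Part 2 compares 50 µg of mRNA-1273.214 with 50 µg of mRNA-1273 (Section 6.2), and all six primary hypotheses in Section 9.2 rest on that contrast. A real departure from the planned dose caused by product concentration would not be random error in a few participants. It would affect the whole test arm, and with it every Part 2 immunogenicity and safety comparison.

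The plan's participant-level safeguards would not detect it:

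- The planned-dose criterion for the Per-Protocol Set for Immunogenicity (Protocol Section 9.5, SAP Section 5.4) and the tracking of dose deviations (Protocol Section 8.12) work one participant at a time. Read literally, the criterion would remove the entire arm in the 25 µg case and nobody for this reason otherwise.
- The accountability log in Section 6.3.5 covers receipt, inventory, dispensing and return or disposition. Section 6.4 covers doses administered. Neither lists product concentration.

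SAP Section 6.4.1 describes Part 2 randomization in the past tense, so what remains open is what the study report can say about the dose in the test arm.

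**Working it through.** The check is dose (µg) = concentration (mg/mL) × 1000 × volume (mL). Volumes and doses come from Protocol Section 6.3.1, concentrations and fill volume from Section 6.3.3.

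**1. The product that reproduces.** mRNA-1273.529: 0.2 × 1000 × 0.25 = 50 µg. Stated: 50 µg. Ratio 1.0.

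**2. The product in question, concentration taken as total mRNA.** mRNA-1273.214: 0.1 × 1000 × 0.25 = 25 µg. Stated: 50 µg. Ratio 25/50 = 0.5. Put the other way, 50 µg in 0.25 mL implies 50/0.25 = 200 µg/mL = 0.2 mg/mL, and 50 µg at 0.1 mg/mL implies 50/100 = 0.5 mL. These restate the mismatch and are not proposals.

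**3. The same product, concentration taken as each mRNA (an assumption).** 2 × 0.1 × 1000 × 0.25 = 50 µg, 25 µg of each. Ratio 1.0.

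**4. Does the composition text decide between 2 and 3?** No. A 1:1 ratio holds equally at 0.1 mg/mL in total (0.05 mg/mL of each) and at 0.1 mg/mL of each (0.2 mg/mL in total).

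**5. Is the per-component reading possible?** Yes. The control's concentration is not stated, but its volume and dose imply 50/0.25 = 200 µg/mL = 0.2 mg/mL. Equal volumes of two 0.2 mg/mL solutions would hold 0.1 mg/mL of each mRNA.

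**6. What evidence would separate the readings?** With the 0.8 mL nominal fill:

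| Product and basis | mRNA per vial | 0.25 mL volumes per vial |
|---|---|---|
| mRNA-1273.529 | 0.2 × 1000 × 0.8 = 160 µg | 0.8/0.25 = 3.2 |
| mRNA-1273.214, total basis | 0.1 × 1000 × 0.8 = 80 µg | 3.2 |
| mRNA-1273.214, per-component basis | 2 × 0.1 × 1000 × 0.8 = 160 µg | 3.2 |

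A labelled vial content would tell the two readings apart. Counting injections per vial would not, because the count is the same on either basis.

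**The case against.** The strongest reply is that this is an ambiguity, not a proven contradiction. The per-component reading fits all three figures without changing any of them, and steps 4 and 5 show that it is compatible with the 1:1 description. The parallel wording used for mRNA-1273.529 is no evidence against it: that product has one mRNA, so its total and per-mRNA concentrations are the same. The 0.1 mg/mL figure also sits in a packaging description that the Pharmacy Manual or commercial packaging may override, while the preparation section states volume and dose directly. The manual's absence from the reviewed documents is not a fault of the plan. Since no dosing error is shown and randomization is past, a low-priority clarification might seem enough.

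Much of this stands. The per-component reading is plausible, the parallel wording settles nothing, and no effect on dosing has been shown. The participant counts are also planning figures: the Amendment 2 summary of changes says few participants were randomized to a 3rd dose, and the primary analysis set is narrower than all 4th-dose recipients.

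The defect in the text remains. Two current sections of the protocol agree only under an assumption that neither document states, and no superseding value is given. The test-arm dose is too basic to Part 2 for the report to rest on an inference.

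**Conclusion.** The concern holds as a discrepancy in the text. For mRNA-1273.214 it is a factor of 2 if 0.1 mg/mL is total mRNA and nil if it is per component. The documents neither state nor exclude the second reading. The planned dose level itself is consistently 50 µg; what is unsettled is the volume, the concentration or the basis of the concentration.

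An effect on the amount administered is not shown. The possible range runs from none to a factor of 2 (50 µg down to 25 µg). The lower end needs all of the following: the volume and concentration are both right as printed, the basis is total mRNA, and no Pharmacy Manual or packaging update supersedes them. If it applied, it would cover the whole test arm: by the planning tables about 1462 participants, 1328 of them in the 4th-dose subgroup on which the primary objective is based.

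It should be fixed whether or not any dosing was affected, because every Part 2 comparison relies on the stated test-arm dose.

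**What to change.** 1. Reconcile Protocol Sections 6.3.1 and 6.3.3 with each other, the Pharmacy Manual and the product label so that volume, concentration and dose agree. State whether the concentration is total mRNA or per component. Which figure is right is for the sponsor to establish; this review proposes none.
2. Before the study report describes the test arm's dose, confirm what was administered and report it. Use existing documentation of the supplied product's concentration or vial content (label, batch records, Pharmacy Manual) together with the eCRF and accountability records. The latter two are not sufficient alone, because the protocol does not list concentration among their contents.
3. If the check shows an arm-wide difference from the planned dose, report it explicitly. Do not leave it to per-protocol exclusions or individual deviation tracking.

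The cost is a protocol clarification and a check of existing records. No new participants, visits or procedures are needed. If the records confirm a per-component basis, a short clarifying phrase is enough for the text.
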